8.3 Association of Adverse Events with Receipt of Study Vaccine

All AEs will have their possible relationship to study vaccine. Causality will be assessed by the PI or designee using the following definition:

Definitely related:	Clear-cut temporal association, and no other possible cause.
Probably related:	Reasonable temporal association and a potential alternative cause is not apparent.
Possibly related:	Less clear temporal association; other causes also possible.
Unlikely related:	Temporal association between the AE and the vaccine or the nature of the event is such that the vaccine is not likely to have had any reasonable association with the observed illness/event (cause and effect relationship improbable but not impossible).
Not Related:	The AE is completely independent of vaccine administration; and/or evidence exists that the event is definitely related to another cause.

The degree of certainty with which an AE can be attributed to administration of the study vaccine will be determined by how well the event can be understood in terms of 1 or more of the following:

1. The event being temporally related with vaccination.
2. A reaction of similar nature having previously been observed with this type of vaccine and/or formulation.
3. The event having often been reported in the literature for similar types of vaccines.

8.4 Assessment of Severity

All AEs will be graded for severity.

- **Solicited AEs will be assessed using the grading system shown in Appendix B: Local and Systemic Adverse Event Grading Systems. This table is based on the NIAID “Division of AIDS (DAIDS) Table for Grading the Severity of Adult and Pediatric Adverse Events,” Version 2.1, March 2017:**
<https://rsc.tech-res.com/docs/default-source/safety/daids-ae-grading-table-.pdf>

- All AEs will be assessed by the study investigators using the grading system shown in Table 2, below:

Table 2: Adverse Event Grading System

Severity	Grade	Defined
None	0	N/A
Mild	1	No effect on activities of daily living, over the counter treatment given $\leq 2x/day$
Moderate	2	Partial limitation in activities of daily living (can complete $\geq 50\%$ baseline, or treatment given $>2x/day$)
Severe)	3	Activities of daily living limited to $<50\%$ of baseline. Medical intervention often required.
Life-threatening	4	Inability to perform basic self-care functions OR severity of illness requires hospitalization

Severity of fever will also be assessed by degree

Table 3: Fever Grading System

Intensity	Grade	Defined
$<100.4^{\circ}\text{F} (<38.0^{\circ}\text{C})$	0	Fever (oral) Temperatures $\geq 100.4^{\circ}\text{F}$, will be confirmed by repeating temperature after waiting 20 minutes
$\geq 100.4^{\circ}\text{F} - 101.4^{\circ}\text{F} (\geq 38.0^{\circ}\text{C} - 38.6^{\circ}\text{C})$	1	
$\geq 101.5^{\circ}\text{F} - 102.4^{\circ}\text{F} (38.7^{\circ}\text{C} - 39.1^{\circ}\text{C})$	2	
$>102.4^{\circ}\text{F} (>39.1^{\circ}\text{C})$	3	

8.5 Investigator Reporting Responsibilities

8.5.1 Adverse Event Reporting

The Office of Clinical Research Policy and Regulatory Operations (OCRPRO) (DCR/NIAID/NIH) is the Sponsor for the IND filed at the U.S. FDA. AE data will be submitted to the IND Sponsor when requested for periodic safety assessments, review of IND annual reports, review of IND safety reports, and preparation of final study reports.

In the interest of subject safety in OCRPRO-sponsored studies and to fulfill regulatory requirements, any deaths and life-threatening SAEs due to any cause that occur during the course of the study must be reported to the OCRPRO Clinical Safety Office (CSO) by the PI within 1 business day after the clinical site becomes aware of the event, and all other SAEs must be reported as soon as possible, but no later than 3 business days after site awareness. SAEs (regardless of relationship and whether or not they are also UPs) must be reported on the Safety Expedited Report Form and sent to the CSO by fax or email attachment.

SAEs that have not resolved by the end of the 3-month follow-up period are followed until final outcome is known. If it is not possible to obtain a final outcome for an SAE (e.g., the subject is lost to follow-up), the reason a final outcome could not be obtained will be recorded by the investigator on the AE case report form (CRF) and the Safety Expedited Report Form (SERF).

SAEs will be reported to:

- Sponsor, OCRPRO, CSO: Mailing address: Clinical Safety Office, [name], [contact], [contact], Email: [contact]
- [name], [contact]; Email: [contact]
- JHSPH IRB [contact], Toll-Free: [name], [contact], Email: [contact]. JHSPH IRB will be notified according to its guidelines, and unexpected AEs that are probably, possibly, or definitely related to the vaccine and meet other JHSPH IRB reporting criteria will be reported in the manner specified by JHSPH IRB.
- The Johns Hopkins University (JHU) Institutional Biosafety Committee (IBC): [contact], [contact]. The JHU IBC will be notified of all SAEs by telephone (followed by written report), email, or fax within 1 working day of notification of the SAE occurrence.

Following notification from the PI, the OCRPRO CSO, as the representative of the IND Sponsor, will report AEs that are serious, unexpected, and related (possibly, probably, or definitely) to the vaccine to the FDA within 15 calendar days of such determination. The FDA will also be notified by phone or fax of all deaths and life-threatening SAEs that are unexpected and related to the vaccine within 7 calendar days, followed by a formal Safety Report within 15 days after being informed of the event. All SAEs and non-serious AEs will be reported to the FDA at least annually in a summary format.

8.5.2 Unanticipated Problems

Non-Serious AEs that are UPs must also be reported on the SAE/UP Report Form and sent to the CSO by fax or e-mail attachment no later than 7 calendar days of PI awareness of the event. The UPs that are not AEs are not reported to the Sponsor CSO.

8.5.3 Pregnancy

All pregnancies through study day 90 will be reported on the Pregnancy Notification/Outcome Form to the CSO within 1 business day from site awareness.

Pregnancy itself is not an AE. However, complications of pregnancies are AEs and may be Serious Adverse Events (SAEs). Events that meet SAE criteria during pregnancy, delivery, or in the neonate (e.g., congenital anomaly/birth defect) are reportable on the SERF.

Pertinent obstetrical information for all pregnancies will be reported to the Clinical Safety Office (CSO) via fax or email within 3 business days from site awareness of the pregnancy.

Pregnancy outcome data (e.g., delivery outcome, spontaneous or elective termination of the pregnancy) will be reported to the CSO within 3 business days of the site's awareness on a protocol-specified form.

Pregnancy events will also be reported to the JHSPH IRB.

8.5.4 Reporting Responsibilities to the JHSPH IRB

In accordance with JHSPH IRB policy, all unexpected SAEs will be reported by the PI within 10 working days of being detected; expected SAEs will be reported annually. All local and systemic reactions not meeting the criteria for SAEs will be captured on the appropriate source documents and entered in CRIMSON, followed to resolution, and reported annually to the FDA and JHSPH IRB.

8.6 Sponsor's Reporting Responsibilities

Suspected unexpected serious adverse reactions (SUSARs) as defined in 21 CFR 312.32 and determined by the Sponsor will be reported to FDA as IND Safety Reports.

The Sponsor will also submit an IND Annual Report of the progress of the investigation to the FDA as defined in 21 CFR 312.33.

8.7 Halting Rules

Halting the study requires immediate discontinuation of study agent administered for all subjects and suspension of enrollment until a decision is made whether or not to continue enrollment and study agent administration.

The PI will closely monitor study data as they become available and will make determinations regarding the presence and grading of AEs. The AEs will be evaluated with regard to the known complications associated with administration of vaccine components. If any of the following events occur, vaccinations will be suspended until the events are reviewed with the study Sponsor (OCRPRO):

1. One or more subjects experience an SAE as defined in Section 8.1.6 of this protocol that is determined to be possibly, probably, or definitely related to the vaccine, **or**
2. One or more subjects experience a hypersensitivity reaction that is probably or definitely related to the vaccine, **or**

3. Any severe clinical illness occurs that is not explained by a diagnosis that is unrelated to vaccination, **or**
4. Two or more subjects in any cohort experience any Grade 3 systemic AE that is determined to be possibly, probably, or definitely related to the vaccine as defined in this protocol.

The IRB, the NIAID, The Gates Foundation, the FDA, or other government agencies, may discontinue the study at any time. Subsequent review of serious, unexpected, and related AEs by the IRB, the IND sponsor, the FDA, and other regulatory authorities may also result in suspension of further administration of vaccine at the clinical site. The FDA, other regulatory authorities, and the study sponsor(s) retain the authority to suspend additional enrollment and administration of vaccine for the entire study as applicable.

The IND Sponsor, in collaboration with the PI will determine if it is safe to resume the study.

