8.1.6 Serious Adverse Events

A SAE is an AE, whether considered related to the investigational vaccine or not, resulting in one of the following outcomes:

1. Death during the period of protocol-defined surveillance.
2. Life threatening event: defined as an event that places a subject at immediate risk of death at the time of the event and does not refer to an event that hypothetically might have caused death were it more severe.

3. Requires hospitalization or prolongation of a hospitalization during the period of protocol-defined surveillance: defined as at least an overnight stay in the hospital for treatment that would have been inappropriate if administered in the outpatient setting.
4. Results in a congenital anomaly or birth defect.
5. Results in a persistent or significant disability or substantial disruption of the ability to conduct normal life functions.
6. Any other important medical event that may not result in death, be life threatening, or require hospitalization, may be considered a serious AE when, based upon appropriate medical judgment, the event may jeopardize the subject and may require medical or surgical intervention to prevent one of the outcomes listed above.

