Headache	No interference with activity	Repeated use of non-narcotic pain reliever > 24 hours or some interference with activity	Significant; any use of narcotic pain reliever or prevents daily activity	ER visit or hospitalization
Fatigue/Malaise	No interference with activity	Repeated use of non-narcotic pain reliever > 24 hours or some interference with activity	any use of narcotic pain reliever or prevents daily activity	ER visit or hospitalization
Myalgia	No interference with activity	Repeated use of non-narcotic pain reliever > 24 hours or some interference with activity	any use of narcotic pain reliever or prevents daily activity	ER visit or hospitalization

* Subject should be at rest for all vital sign measurements.

** When resting heart rate is between 60 – 100 beats per minute. Use clinical judgment when characterizing bradycardia among some healthy subject populations, for example, conditioned athletes.

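### Halting rule 4 counts Grade 3 but not Grade 4 systemic events, so read literally two ER-visit reactions in a cohort do not meet it although two milder ones do

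*Combined protocol and SAP*

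**What the plan says.** Section 8.7 lists four events that suspend vaccination pending review with the sponsor. Rule 1 is one related serious adverse event. Rule 2 is one related hypersensitivity reaction. Rule 3 reads "Any severe clinical illness occurs that is not explained by a diagnosis that is unrelated to vaccination". Rule 4, the only one that counts events by numeric grade, applies when "Two or more subjects in any cohort experience any Grade 3 systemic AE that is determined to be possibly, probably, or definitely related", meaning vaccine-related.

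Appendix B Table 5 grades systemic events. For headache, fatigue/malaise and myalgia the Grade 4 entry is "ER visit or hospitalization", with no further condition. Grade 3 for headache is "Significant; any use of narcotic pain reliever or prevents daily activity", and malaise and myalgia are similar. Grade 2 for all three is "Repeated use of non-narcotic pain reliever > 24 hours or some interference with activity".

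Section 8.1.6 defines a serious event. Item 2 requires "an event that places a subject at immediate risk of death at the time of the event" and excludes hypothetical risk. Item 3 requires "at least an overnight stay in the hospital for treatment that would have been inappropriate if administered in the outpatient setting". Item 6 is discretionary: "Any other important medical event that may not result in death, be life threatening, or require hospitalization, may be considered a serious AE" on medical judgment.

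On which scale applies, 8.4 assigns solicited events to Appendix B and, in its next bullet, assigns all adverse events to Table 2 without excepting the solicited ones. Section 8.2 says that solicited non-serious events may be graded by a different table where the protocol specifies one.

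**The concern.** A count trigger should be monotone in severity: if two events of a given grade stop vaccination, two worse events should too. As worded, rule 4 is not. The site applies it while vaccinations are still being given, and the principal investigator makes the grading determinations. Someone following the text exactly could record two related ER visits for headache or myalgia in one cohort and conclude that rule 4 is not met. What is at stake is whether further healthy volunteers are vaccinated before the sponsor has looked at those events.

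The overlap between the two grading scales adds a smaller uncertainty, because it can change whether a given event is called Grade 3 or Grade 4.

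**Working it through.** The protocol gives no operating characteristics for the halting rules, so there is no stated figure to reproduce. The check is mainly textual.

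**Step 1: which solicited systemic events are affected.** Section 8.1.2 lists five: fever, headache, malaise, nausea and myalgia. In Table 5 an ER visit alone is Grade 4 for headache, malaise and myalgia. For nausea, Grade 4 is tied to hypotensive shock. Fever is graded in Table 3, where the top grade is 3 and has no upper limit. So 3 of 5 are affected.

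**Step 2: the rule 4 count, read literally, for two subjects in one cohort with related events.**

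| Two subjects, graded by Table 5 | Count | Rule 4 |
|---|---|---|
| Grade 3 and Grade 3 (e.g. a narcotic taken for headache at home) | 2 | met |
| Grade 3 and Grade 4 (ER visit only) | 1 | not met |
| Grade 4 and Grade 4 (both ER visit only) | 0 | not met |

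**Step 3: whether another rule closes the gap.**

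- Rule 1, item 2 of 8.1.6: needs immediate risk of death. The column label in Table 5 (potentially life threatening) does not supply that.
- Rule 1, item 3: needs an overnight stay. An ER visit with discharge does not meet it.
- Rule 1, item 6: can be met, but only if the investigator so judges.
- Rule 2: relevant only if the event is a hypersensitivity reaction.
- Rule 3: can be met by a single event, but severe clinical illness is not defined.

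An ER-only event is therefore reached by judgment, not automatically.

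**Step 4: where the two grading scales differ.** Table 2 sets Grade 3 at daily activity below 50% of baseline, and Grade 4 at loss of basic self-care or illness requiring hospitalization.

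| Event | Table 5 | Table 2 |
|---|---|---|
| (a) Headache, malaise or myalgia, any narcotic, activity at 50% or more | Grade 3 | at most Grade 2 |
| (b) Malaise or myalgia, activity below 50% but not prevented, no narcotic | arguably Grade 2 | Grade 3 |
| (c) ER visit only, activity below 50%, self-care retained | Grade 4 | Grade 3 |

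In case (c) the event counts toward rule 4 by Table 2 and, read literally, does not by Table 5. Confirming Appendix B without adding *or higher* would therefore make the gap certain.

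**Step 5: what the rewording does to the chance of a pause (illustration only).** The event rates below are assumptions; the documents give none. Each subject is classified by worst related systemic grade, subjects are independent, the rate is the same in both cohorts, and only rule 4 is considered. For a cohort of n with rate p, P(n, p) = 1 − (1 − p)^n − n·p·(1 − p)^(n−1). For either cohort, 1 − [1 − P(n1, p)]·[1 − P(n2, p)]. As written, p is the Grade 3 rate; reworded, p is the sum of the Grade 3 and Grade 4 rates.

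With n1 = 15, n2 = 20, Grade 3 at 2% and Grade 4 at 1%:

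- As written: P(15, 0.02) = 0.0353 and P(20, 0.02) = 0.0599, so 1 − 0.9647 × 0.9401 = 0.093.
- Reworded: P(15, 0.03) = 0.0730 and P(20, 0.03) = 0.1198, so 1 − 0.9270 × 0.8802 = 0.184.

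| Assumed Grade 3 / Grade 4 rate | 15 and 20: as written → reworded | 12 and 20: as written → reworded |
|---|---|---|
| 2% / 1% | 9.3% → 18.4% | 8.2% → 16.3% |
| 5% / 2% | 39.0% → 57.9% | 35.1% → 53.2% |
| 0% / 5% | 0% → 39.0% | 0% → 35.1% |

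The last row shows the gap in isolation: if all the severe reactions are Grade 4, rule 4 as written never fires.

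**The case against.** The strongest reply is that grades are ordinal and any safety reviewer would read a Grade 3 trigger as including Grade 4. A subject whose headache leads to an ER visit will often also have been prevented from daily activity, which is itself a Grade 3 criterion. That is probably the intent, and it makes this a wording correction, but the text does not state it.

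Second, the other rules are substantial. Rule 3 can act on a single event, severe is the label for Grade 3 in both scales, and an event judged vaccine-related has no unrelated diagnosis to exempt it. An event in a column headed potentially life threatening is also a natural candidate for item 6 of 8.1.6. The sponsor and the FDA can suspend at any time, and a Medical Monitor oversees safety. This stands as a reason why the effect is limited. It does not close the gap: item 6 is discretionary, and if rule 3 covered every reaction graded severe, the two-subject threshold in rule 4 would be largely redundant.

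Third, two related ER-only reactions in one cohort of 12 to 20 healthy adults after one dose of inactivated vaccine are unlikely. Section 11.4.3 reports the vaccine as generally well tolerated, with 84% of reported adverse events mild and few severe. This also stands.

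A reader might infer from 8.4 that there is no indication which scale governs solicited events. The documents do not support that. Section 8.2 allows a different table where one is specified, and 8.4 then specifies Appendix B in mandatory terms, so the specific assignment is the natural reading. What remains is that the Table 2 bullet makes no exception and that neither section says which grade feeds rule 4.

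**Conclusion.** The point holds as a wording gap in rule 4. Under Table 5 grading and a literal reading, two related ER-only events, or one together with a Grade 3 event, do not meet the rule, although two milder Grade 3 events do. This concerns three of the five solicited systemic events. Fever and injection-site reactions are not affected.

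It would go too far to infer that Grade 4 events escape the halting rules as a whole. Rule 1 catches related life-threatening events and overnight admissions, rules 1 and 3 are likely to catch most Grade 4 events, and rule 4 leads only to a pause for sponsor review. The question of which scale governs is secondary, since the text already points to Appendix B.

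No probability can be attached to the gap, because the documents give no Grade 3 or Grade 4 rates. The safety review and communications plan mentioned in 8.8 is not among the documents, so whether it settles the grading cannot be checked. The correction is still worth making: it concerns a stated safety threshold and costs almost nothing.

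**What to change.** In 8.7, rule 4, change the trigger to *Grade 3 or higher*.

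In 8.4, add one sentence: Appendix B governs every event or vital sign it lists, solicited or not; Table 3 governs fever; Table 2 governs adverse events listed in neither; and these grades are the ones used for rule 4. The words *solicited or not* matter, because Table 5 also grades heart rate, blood pressure and respiratory rate, which are not solicited events. Limiting Appendix B to solicited events would move them to the activity scale in Table 2 and leave their numeric thresholds unused.

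Make both edits together, since settling on Appendix B alone would lock in the gap. The cost is one line in each section, with no new data or visits. The downside is a higher chance of a precautionary pause. Its size depends on the unknown rates and need not be small, as the illustration shows, but every pause added by *or higher* would involve at least one related Grade 4 event.

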8.8 Safety Review and Communications Plan

A safety review and communications plan (SRCP) has been developed for the protocol. The SRCP is an internal communications document between the PI and the CSO, which delineates the safety oversight responsibilities of the PI, the CSO, and other stakeholders. The SRCP also includes the overall plan for conducting periodic safety surveillance assessments.

8.9 Sponsor Medical Monitor

A Medical Monitor, representing the IND Sponsor (OCRPRO), has been appointed to provide safety oversight of this clinical study. The Sponsor Medical Monitor will be responsible for performing safety assessments as outlined in a Safety Review and Communication Plan.

The PI is responsible for ensuring that the Safety Monitor is aware of all new safety information during the course of the clinical trial.

9. DATA COLLECTION AND MONITORING

9.1 Source Documentation

Complete source documentation (laboratory test reports and/or medical records) is required for every study subject for the duration of the study. Specified data from source documentation for subjects enrolled in the study will be entered into the CRIMSON data system. The data entry is to be completed on an ongoing basis during the study. Data entered into CRIMSON shall be performed by authorized individuals. Corrections to the data system shall be tracked electronically (password protected) with time, date, individual making the correction, and what was changed. Source documentation should support the data collected in CRIMSON and must be signed and dated by the person recording and/or reviewing the data.

The PI is responsible for the accuracy, completeness, and timeliness of the data reported to the Sponsor through the CRIMSON Data System. All data entered into CRIMSON

should be reviewed by an Investigator and signed as required with written or electronic signature, as appropriate. Data reported in CRIMSON should be consistent with source documents or the discrepancies should be explained. Source documentation will be made available for review or audit by the Sponsor or designee and any applicable Federal authorities.

9.2 Study Documentation

Study-related documentation will be completed as required by the IRB, the Sponsor, and regulatory authorities. Continuing review documentation will be submitted by the PI to the IRB on the anniversary date of initial review as specified by the IRB. An annual report will be submitted by the Sponsor to the FDA within 60 days after the anniversary date that the IND for this study went into effect. The annual report will provide a brief description of the progress of the investigation as outlined in 21 CFR 312.33, and will discuss any revisions that have been made to or are planned for the protocol.

The PI will maintain adequate records of the disposition of the investigational product, including dates of receipt and disposition, administration, quantity, and use by subjects. If the study is terminated, suspended, or completed, all unused supplies of the investigational product will be destroyed by the investigational pharmacy staff.

